This project is a pilot study Virtual Reality mindfulness and wellbeing study, the medical statistician will be an independent person, [name] and [name]. The DMC will meet by Skype or teleconference as much as possible for sustainability. However, if there are number of any adverse events or serious adverse events reported such as severe dizziness, severe skin rashes, severe confusion related to the VR application, the data will be looked into at any time of the study period. Procedure will be conducted in accordance with MHRA Good Clinical Practice Guide. The committee will have full access to the anonymous data after approximately 10% to 25% of participants have been recruited. The aim of the DMC is to identify any safety issues that may give cause for concern and to inform the study Steering Committee (including early study termination, if required). The DMC will meet before the Steering Committee (SC) meeting and the minutes from the DMC will be forwarded to the SC for their consideration. The role of the committee will be to monitor and advise the study safety.

Steering Committee

The Steering committee will be independent to the DMC. The plan for steering committee to meet at least once to make sure that there are no reports of an unexpected events such as severe confusion, severe dizziness unable to recover which requires emergency admission due to VR application during the study period. The committee will be chaired by the Clinical surgical experts, [name], and a lay person, all of whom will be completely independent of the study. The lay person who is our previous heart patient who sits on a Ticker club (heart charity club) at Wythenshawe hospital will be given full training about this study.

ABBREVIATIONS

3D 3 Dimensions

GP General Practitioner

STAI State Trait Anxiety Inventory

[figure not shown]
VAS Visual Analogue Scale

VR Virtual Reality

STUDY FLOW CHART

STUDY PROTOCOL

1 Abstract

Background (Lay):

Non-drug methods like hypnosis and Virtual Reality (VR) are used alongside other treatments to help patients with anxiety and different types of pain. But when it comes to using VR to help people who are having heart surgery, there haven't been many studies. One reason for this might be that using VR for this purpose is relatively new, VR technology is changing quickly, and it can be expensive to get started with VR.

Scientific

The use of mindfulness and relaxation techniques such as immersion in nature and natural landscapes is steadily rising in the clinical care [1]. Different non-pharmacological techniques, including hypnosis and immersive virtual reality (VR) are currently used as complementary tools in the treatment of acute and chronic pain. Anxiety, stress are other common problems for patients undergoing cardiac surgery. [1,2,3] Many practices have sought to develop nonpharmacologic strategies to ameliorate preoperative stress, anxiety and pain. Hendricks et al. showed that in post-cardiac surgery patients immersive VR significantly reduced multiple measures of state anxiety compared with baseline, including feeling tense, strained, and upset.[4]. However, the control group in their study had an intervention of tabletop games and standard care was not measured within either group.

Aims and objectives:

This pilot study will assess immersive head mounted VR simulations in adult patients undergoing first time elective cardiac surgery to understand the impact on patient anxiety and stress. The primary objective is to assess anxiety and stress levels between two groups.

Methods:

Cardiac surgery patients (n = 30) undergoing first time elective/urgent-in-patient cardiac surgery at Wythenshawe Hospital site will be randomly assigned equally to two arms (control with control or VR) using a computer-generated randomisation list. The control group will receive standard care admission process which includes a surgical information booklet, online Microsoft Teams experiential talk about the surgery pathway by a heart charity and two sessions of 15 minutes music session with WorWoder Wireless blue tooth headset as a control pre- and post-surgery as same timings as intervention group. The VR intervention group will receive the same as the control group with the addition of two VR sessions: session one 15 minutes VR session will be one hour before surgery and sessions two on day 3 evening (around 6pm) postoperatively. Patients who are ventilated on day 3 will be removed from the study and additional patients will be recruited on both groups. Questionnaires will be handed to the patients pre- and post-surgery in both groups to rate their levels of anxiety and stress level (STAI), physiological assessments, VR experience and VR-absorption (VAS) in intervention group will be recorded.

In addition, we will explore if there is association between salivary cortisol levels as a potential biomarker for stress and self-completed questionnaires anxiety level (STAI). We will obtain four samples of before and after control/VR intervention pre- and post-surgery to see the co-relation.

Expected outcomes:

This study will identify whether the use of VR technology has the potential impact to reduce pre and post operative anxiety and stress.

2. Research Question

- 1. Can immersive head mounted Virtual Reality headset intervention reduce pre-and postoperative anxiety and stress in adult patients undergoing elective cardiac surgery?
- 2. Is the use of VR technology being feasible immediate post-surgery on cardiac surgery patients?

3 Objectives and Outcomes assessments

2.1 Primary Objectives:

Assessment of anxiety, stress levels between two groups

2.2 Secondary Objectives:

- Feasibility of VR technology.
- Correlation between cortisol level and STAI
- VR experience
- VR absorption

2.3 Outcome Measures:

- **Primary outcome:** patients' anxiety and stress levels four time points (before and after each session on pre- and post-surgery (STAI)
- Secondary outcomes:
- Cortisol swabs four time points (before & after each session on pre- and post-surgery).
- Physiological parameters pre- and post-surgery.

For intervention group only:

- Patient experience about VR (Rescape™ company questionnaire))
- VR Absorption and immersion scale (VAS 0-10)
- Proportion of patients consenting to VR.
- Proportion of patients completing the VR sessions.
- Adverse events due to VR.

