Absorption is the "tendency to become fully involved in a perceptual, imaginative, or ideational experience". We will ask the intervention subjects to answer this question: "Could you estimate on a 0- (not at all) to 10- (fully) scale how deeply you felt absorbed and felt your attention as focalised and focused by the experience you have just lived?". Immersion and presence will be assessed using a Visual Analogue Scale. The questions will be of the form "from 0 to 10, how much did you feel present in the environment?"

Cortisol assay:

Both group patients will have 4 samples, before and after control/VR intervention pre- and postsurgery which will give a total of $4 \times 30 = 120$ samples.

Sample collection:

- Salivary cortisol is considered a reliable and valid measure of unbound or free cortisol levels in plasma. Oral swabs (30 x 10mm cylinder) and salivette storage tubes will be used to collect samples from the participants. During collection, participants will be instructed to place the swab under their tongue on the floor of the mouth for 1-2 minutes. Swabs will be placed in salivettes and within an hour after collection, stored in a lab freezer below -20°C. The storage, transport and testing procedures or the samples will be subject to standard practice and all usual risk assessment procedures as per MFT hospital.

Analysis:

The Cortisol free in Salvia ELISA kit will be used to determine the concentration of cortisol in the samples. Upon the receipt of the samples, they will be immediately stored at -20°C until analysis. The frozen samples will be thawed and centrifuged for 5 to 10 minutes at 2000-3000 x g. Of the standard and reagent, the control reagent, and the saliva sample,50 µL will be dispensed in microtiter wells, as well as 50 µL of a cortisol-horseradish peroxidase conjugate for binding to the coated antibody. The wells will be incubated for 60 minutes at room temperature. Afterwards, they will be rinsed 3 times with 300 µL diluted wash solution and 200 µL of substrate solution will be added. Again, the wells will incubate for 30 minutes at room temperature and 50 µL of stop solution will be added to each well. The absorbance of each well will be determined with the use of a microtiter plate calibrated reader at 450 \pm 10 nm within 15 minutes.

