6.2 Sample size and power calculation

Sample size has been determined on pragmatic grounds and rule of thumb for pilot studies. 15 patients are required in each group giving a total of 30 patients. We decided to enrol 10% more to compensate for dropouts after the surgery making the total 34 patients.

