8 STUDY MANAGEMENT

8.1 Protocol compliance

- If the patient refuses to participate any more follow-up postoperatively on day 3, they will be terminated and withdrawn from the study, but we will use the pre-operative collected data.
- We will try to minimise, and every effort will be taken to obtain any missing data. If it occurs which will be recorded and reported appropriately.

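### Patients ventilated on day 3 are removed after randomisation and replaced, with no rule for their pre-surgery data, the completion denominator or the enrolment limit

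*Protocol*

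**What the plan says.** The rule stands in the Abstract, Methods: "Patients who are ventilated on day 3 will be removed from the study and additional patients will be recruited on both groups". The same paragraph gives the number randomised: "Cardiac surgery patients (n = 30) undergoing first time elective/urgent-in-patient cardiac surgery at Wythenshawe Hospital site will be randomly assigned equally to two arms". Elsewhere the rule appears only indirectly, in section 6.3, which promises the number and percentage removed for ventilation and, as a separate line, the number and percentage not completing a VR session for any reason.

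Four other places bear on it:

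- Section 8.1, on patients who refuse follow-up on day 3: "they will be terminated and withdrawn from the study, but we will use the pre-operative collected data".
- Section 6.2, after stating that 30 patients are required: "We decided to enrol 10% more to compensate for dropouts after the surgery making the total 34 patients".
- Section 6.1, Cortisol assay: "Both group patients will have 4 samples, before and after control/VR intervention pre- and postsurgery which will give a total of" 120, worked out there as 4 × 30.
- Section 2 asks: "Is the use of VR technology being feasible immediate post-surgery on cardiac surgery patients". The matching outcome, listed for the intervention group only, is "Proportion of patients completing the VR sessions". No denominator is given.

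**The concern.** Removal depends on an event after surgery. Session one differs by arm and takes place before surgery, so by day 3 the patient has been randomised and would normally have completed session one with its before-and-after STAI, cortisol and vital signs. Ventilation on day 3 cannot have altered those values, so it is no reason to lose them. The natural reading of removal from the study is that they are lost.

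The second research question makes this more than a matter of tidiness. Being unable to use a headset because of ventilation is part of the answer to whether VR is feasible soon after cardiac surgery. A rule that takes out such patients and brings in others invites a completion proportion calculated only among those who could use it.

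Replacement also leaves enrolment open. The wording does not say whether one removal leads to one recruit or to one in each arm, how recruits are placed on the randomisation list, or whether they come out of the extra places already allowed for losses after surgery. In a pilot of about 15 per arm, one patient is 1/15, or about 7%, of an arm.

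**Working it through.** **1. The plan's own figure.** Inputs from section 6.2: 30 required, 10% allowance. 30 / (1 − 0.10) = 33.3, rounded up to 34. Per arm, 15 × 1.10 = 16.5, rounded up to 17, and 2 × 17 = 34. The figure reproduces, and 30 required with 34 enrolled is coherent within section 6.2.

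**2. What a ventilated patient has already given.** Sections 5 and 6.1 place session one within an hour of surgery and the first two STAI and cortisol sets around it. Two of the four primary-outcome time points therefore precede the event that triggers removal.

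**3. Two kinds of day-3 loss side by side.**

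| | Refuses on day 3 (section 8.1) | Ventilated on day 3 (Abstract) |
|---|---|---|
| Status | withdrawn | removed |
| Pre-surgery data | used | not stated |
| Replaced | not stated | yes, without a cap |

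**4. Completion in the VR arm.** The documents give no ventilation rate, so the number ventilated is an assumption, shown from one to three. Suppose 15 non-ventilated VR patients all complete. Intervals are exact (Clopper-Pearson).

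| Ventilated in VR arm | Ventilated left out | All randomised to VR |
|---|---|---|
| 1 | 15/15 = 100% (78 to 100%) | 15/16 = 94% (70 to 100%) |
| 2 | 15/15 = 100% (78 to 100%) | 15/17 = 88% (64 to 99%) |
| 3 | 15/15 = 100% (78 to 100%) | 15/18 = 83% (59 to 96%) |

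**5. Enrolment if replacement is separate from the 10% allowance.** Expected enrolment for 30 evaluable patients is 30 / ((1 − p) × 0.90), with p the assumed proportion ventilated on day 3:

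- p = 2%: 34.0
- p = 5%: 35.1
- p = 10%: 37.0
- p = 15%: 39.2

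If the four spare places cover ventilation alone, the binomial chance that more than four of 34 are lost is 0.1%, 2.6%, 25% and 59% at the same rates.

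**6. Cortisol samples.** With 34 randomised and 30 reaching day 3, 30 × 4 + 4 × 2 = 128. With no losses, 34 × 4 = 136. The 120 in section 6.1 equals 30 × 4 and leaves out the four extra patients.

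**The case against.** The strongest reply is that section 6.3 already discloses the losses. Removals for ventilation are reported, VR non-completion is reported for any reason, and dropout proportions carry 95% confidence intervals. A reader could rebuild the proportion over all randomised, and counting non-completion for any reason points towards including ventilated patients. That stands as far as it goes: a reader might infer that the plan necessarily overstates feasibility, but this follows only if removed patients leave the denominator, which the protocol does not fix. Disclosure does not fix it either. Removals are listed apart from non-completion and are not requested by arm, and nothing returns these patients to the session-one comparison.

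Three further inferences are tempting and not supported:

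- *That the pre-surgery data will be deleted.* This is the natural reading of removal, but it is not stated. Section 8.1 shows that in this protocol withdrawal can go together with use of pre-operative data. The fault is silence where section 8.1 is explicit.
- *That the rule necessarily breaks the randomised comparison.* Nothing in the documents suggests that a 15-minute VR or music session affects ventilation on day 3. If ventilation is unrelated to allocation, exclusion costs precision without biasing the arm comparison. Ventilated patients could not complete a day-3 questionnaire under any rule, and section 6.3 calls the analyses mainly descriptive.
- *That 30 against 34 is itself an error, or that losses are compensated twice.* Section 6.2 is coherent. The additional patients in the Abstract may be the four extra places; the documents do not say.

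**Conclusion.** The point holds as a fault in a stated conduct rule, so it cannot simply be left to an analysis plan. Followed as written, the rule removes and replaces randomised patients because of a post-surgery event, leaves their valid pre-surgery data without a stated use, and sets no limit on or allocation method for replacements. The Abstract and the sample count in section 6.1 work from 30 patients, while section 6.2 enrols 34.

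The possible effect on feasibility is 6, 12 or 17 percentage points of completion (100% against 94%, 88% or 83%) with one, two or three ventilated VR patients. This assumes that all 15 others complete and that ventilated patients are left out of the denominator. The true number may be nil: section 5 excludes emergency, complex and redo surgery and critical preoperative state, which may keep it low. Neither bias between the arms nor deletion of data is shown.

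**What to change.** Replace the removal rule in the Abstract and restate its replacement in section 8.1:

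- Every randomised patient stays in the allocated arm for analysis.
- Session-one STAI, cortisol and vital signs are analysed on all randomised patients with data.
- Day-3 outcomes of ventilated patients are recorded as missing, with the reason, by arm.
- Session-two completion is reported over all patients randomised to VR.

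State one enrolment figure throughout: 34 randomised, 17 per arm, to leave about 30 with day-3 data. Say that the 34 covers ventilated patients. Correct the Abstract and section 6.1 to match, with about 128 cortisol samples expected and 136 at most. Any top-up patients take the next slot on the randomisation list and are added to those already randomised, not substituted for them.

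The cost is protocol wording, about 8 more assays than the 120 planned (16 at most), and a completion rate that may look less favourable. Day-3 numbers may also fall short of 30: with 10% total loss among 34, the chance of losing more than four is 25%. For a pilot sized by rule of thumb this is tolerable.

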Patients will be instructed to discontinue use if they experienced any discomfort or side effects (dizziness, motion sickness, etc); this will be recorded as a side effect and limitation of the therapy. Participants will be instructed to refrain from engaging in other video game activities, watching television, or using their phones during the time of intervention to standardise the impact of their assigned intervention.

Session one: Patient will receive the VR session pre surgery within one hour time period of their surgery. Session two: They will receive the VR session on day 3 post surgery (around 6pm).

Hygiene measures:

Two VR headsets (£6000) and two WorWoder Wireless blue tooth headset (£100) will be provided by the company free of cost for this study and it will be used within the hospital premises. Infection control measures will be used as per manufacturer recommendation. Adequate hand hygiene is required upon

handling the device or the controllers. Adequate disinfection of the device between each patient use, includes dismantling of all separable parts and thorough disinfection with non-alcoholic cleaners as per manufacturer's recommendation.

Patients who might not adequately understand verbal explanation or written information given in English will be provided with hospital interpreters. All the patients whose first language is not English will have an interpreter booked by the hospital.

Eligibility criteria are as follows:

All adult cardiac surgery patients will be considered for inclusion in this study regardless of age, disability, gender reassignment, marriage and civil partnership, pregnancy and maternity, race, religion and belief, sex, and sexual orientation except where the study inclusion and exclusion criteria EXPLICITLY state otherwise.

Inclusion criteria:

- Adults undergoing first time elective cardiac surgery (coronary artery bypass surgery and aortic/mitral valve surgeries), age more than 18 years, who will give informed consent for their participation to this study.
- Urgent in patient who are well enough to read and understand the study and patient information leaflet.

Exclusion criteria:

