6.4 Data analyses and Study Stopping Criteria

Data will be analysed at the end of the study. Any serious Major Adverse events such as severe dizziness, severe skin rashes, severe confusion related to the VR application which requires emergency hospital admission/treatment will trigger study stopping criteria and will be discussed immediately at an emergency steering and data monitoring committee. The final clinical data will be analysed at the study end point.

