7 SAFETY REPORTING

We are not expecting any major adverse events for this study. However, if there are any adverse events, including serious adverse events (SAE), that the chief investigator suspects could have been related to procedures in the study protocol will be reported to the study Sponsor.

All adverse event assessments and reporting will be carried out in line with MFT trust and the University of Salford SOP's. The serious adverse events are defined as an adverse event which results in one of the following:

- a. Severe confusion which requires immediate hospital admission and treatment.
- b. Severe dizziness or headache which requires immediate hospital admission and treatment.

 Severe skin or allergic rashes which requires immediate hospital admission and treatment.

Serious adverse events and adverse events will be collected and recorded on the electronic case report form according to the local hospital research protocol.

The main role of the Principal investigator (PI) will report any adverse and serious adverse events:

- a. Using medical judgement in assigning seriousness, causality and whether the event/reaction was anticipated.
- b. Ensuring that all SAE/SARs are recorded by completing the SAE form as soon as possible after becoming aware of the event and send a scanned copy to the University of Salford sponsor office using the email address [contact]
- c. SAE/SARs must be reported to the sponsor office within 24 hours of the research team becoming aware of the event.
- d. Reviewing and reporting the accuracy and completeness of all SAE/AE.
- e. Closely monitoring patients for any new events.
- f. Ensuring a log of all events is kept within the Site File and which may be reviewed by oversight committees such as the Steering Committee.

The Chief Investigator (CI) is responsible for:

- a. Clinical oversight of the safety of patients participating in the trial, including an ongoing review of the risk / benefit.
- b. Using medical judgement in assigning the SAEs/SARs seriousness, causality and whether the event was anticipated where it has not been possible to obtain local medical assessment.
- c. Using medical judgement in assigning whether an event/reaction was anticipated or expected.
- d. Immediate review of all Serious Unexpected Serious Adverse Reactions (SUSARs).

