- e. Review of specific SAEs/SUSARs in accordance with the protocol and trust SOPs on Safety Reporting for Studies other than Clinical Trials of Investigational Medicinal Products (CTIMPs).
- f. The Investigator is expected to maintain a log or spreadsheet of all adverse events and effects (including those reported as serious), which may be reviewed by oversight committees such as the Steering Committee. Any trends must be reported by the Investigator to oversight committees in a timely manner.

7.1: Expected safety reporting.

Cross contamination and patient reported side effects from VR headset use will be reported such as severe nausea, severe dizziness, severe disorientation, severe balance problems, severe headache, severe eye strain, severe fatigue and severe cross infection which requires immediate medical treatment.

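### The adverse-event outcome in section 2.3 is limited to the VR arm and to events judged due to VR, although section 7 collects adverse events with no limit by arm

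*Protocol*

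**What the plan says.** Protocol section 2.3 (Outcome Measures) has a block labelled "For intervention group only". It contains the only adverse-event outcome, "Adverse events due to VR", next to "Proportion of patients completing the VR sessions".

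Other safety text also starts from VR:

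- Section 7.1: "Cross contamination and patient reported side effects from VR headset use will be reported such as severe nausea". A list of further severe symptoms follows.
- Section 6.4: "severe confusion related to the VR application which requires emergency hospital admission/treatment will trigger study stopping criteria".
- Section 5, in the description of the VR arm, on discomfort that makes a patient stop a session: "this will be recorded as a side effect and limitation of the therapy".

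The main text of section 7 is wider. It states "Serious adverse events and adverse events will be collected and recorded on the electronic case report form according to the local hospital research protocol". Its three types of serious event (confusion, dizziness or headache, rash) are not tied to VR. Events go to the sponsor if they are ones "that the chief investigator suspects could have been related to procedures in the study protocol will be reported to the study Sponsor", and study procedures include the music sessions. The investigator also keeps a log of every adverse event, which oversight committees may review. Section 7 leaves causality to medical judgement.

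Section 6.3 reports the number of patients not completing VR sessions for any reason. It names no summary of adverse events.

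**The concern.** The outcome applies two filters before anything is counted: the patient must be in the VR arm, and someone must already have decided that VR caused the event. A music-arm event cannot enter the outcome, even if section 7 has put it on the case report form.

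The attribution filter is weak here. The protocol describes no masking, and a head-mounted display is visibly different from music headphones, so whoever assigns causality will probably know the arm. The second session falls on day 3 after heart surgery, when dizziness, nausea or fatigue may have other causes. A real VR effect could be put down to the operation, or a background symptom put down to VR.

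The trial already has the means to reduce this problem: a randomised music arm with sessions at the same times, assessed before and after each one. Use soon after surgery is the second research question, so the symptom data bear on a main purpose of the pilot.

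**Working it through.** **Inputs.** From section 6.2: 15 patients per arm, 30 in total, 34 enrolled. The documents give no background rate for such symptoms. I assume that a proportion *p* of 10% to 40% of patients would have at least one symptom of any severity without VR, independently of one another.

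**The plan's own figure.** 30 / (1 - 0.10) = 33.3, rounded up to 34, or 17 per arm. It reproduces, and nothing below changes it.

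**Step 1: symptoms expected in the VR arm with no VR effect.** With *n* = 15, the expected number is *np*. The chance of at least one is 1 - (1 - *p*)^15. The chance of at least three is 1 minus the binomial probabilities of 0, 1 and 2. For *p* = 10%: 15 × 0.10 = 1.5, and 1 - 0.9^15 = 0.794.

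| Assumed *p* | Expected of 15 | At least one | At least three |
|---|---|---|---|
| 10% | 1.5 | 79% | 18% |
| 20% | 3.0 | 96% | 60% |
| 30% | 4.5 | over 99% | 87% |
| 40% | 6.0 | over 99% | 97% |

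Across this range some VR patients will probably have a symptom even if VR does nothing. How many of them enter the outcome then depends on the attribution judgement.

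**Step 2: what a count from one arm shows.** Exact (Clopper-Pearson) 95% limits, with illustrative counts:

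- 3/15 = 20%, interval 4.3% to 48.1%
- 5/15 = 33%, interval 12% to 62%
- 0/15: upper limit 1 - 0.025^(1/15) = 21.8%

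None of these can be divided into background and VR effect.

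**Step 3: what the music arm would add.** Newcombe interval for a difference *d* = *p1* - *p2*, built from the Wilson limits (*l*, *u*) of each arm:

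- lower = *d* - √[(*p1* - *l1*)² + (*u2* - *p2*)²]
- upper = *d* + √[(*u1* - *p1*)² + (*p2* - *l2*)²]

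For 3/15 in both arms the Wilson limits are 0.0705 and 0.4519. The half-width is √[(0.2 - 0.0705)² + (0.4519 - 0.2)²] = √(0.0168 + 0.0635) = 0.283.

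| VR | Music | Difference | 95% interval |
|---|---|---|---|
| 3/15 | 3/15 | 0 points | -28 to +28 |
| 5/15 | 3/15 | +13 points | -18 to +41 |
| 5/15 | 1/15 | +27 points | -3 to +52 |

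The same 5/15 in the VR arm reads differently against 3/15 than against 1/15. The intervals are wide, so the contrast describes and does not test.

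**The case against.** The strongest reply is that section 7 already covers the control arm. It collects adverse events without naming an arm, defines its serious events without mentioning VR, and requires a log of all events. A reader might infer from section 2.3 that the trial will have no comparator data at all. The documents do not support that: control events may well be recorded. What stands is that the outcome, as defined, would leave them out, and that the protocol specifies no equal questioning of the two arms after each session.

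A reader might also infer that VR tolerability cannot be judged. That goes too far. Session completion, non-completion for any reason (section 6.3) and side effects that end a session (section 5) all inform tolerability within the VR arm.

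Nor do the documents say that these symptoms are common after heart surgery, so the background rate above is only an assumed range. Sections 6.4 and 7.1 concern severe events needing treatment or admission, and the figures above do not describe those. Section 6.4 gives its events as examples, and the data monitoring committee has access to all anonymised data, so its view is not confined to events attributed to VR.

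Three further points have weight. Tables by arm are often left to an analysis plan, which is not shown here. That excuses missing detail, but the restriction to one arm is a stated rule, and an analysis plan that followed it would omit control events. Patients would still know their arm when answering, so reporting bias is reduced but not removed. And with 15 per arm the gain in precision is small, which is tolerable in a pilot whose analyses are mainly descriptive.

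**Conclusion.** The point holds as a mismatch between the outcome definition and the safety collection, with a consequence for interpretation. Section 2.3 restricts the adverse-event outcome by arm and by attribution, section 7 does not restrict collection by arm, and the two should be reconciled.

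On an assumed background of 10% to 40%, 1.5 to 6 of 15 VR patients would have a symptom with no VR effect, so a VR-only attributed count says little about VR itself. This rests on three assumptions: the background range, independence between patients, and the inference that those judging causality will know the arm.

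It is a cheap improvement that should be made. It is not a flaw that invalidates the pilot or leaves safety unmonitored.

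**What to change.** 1. In section 2.3, move adverse events out of the VR-only block and define the outcome for both arms, in line with section 7.
2. After each session in both arms, ask the same short set of symptom questions at any severity. Adapt the set from section 7.1, and omit items such as cross infection that cannot be assessed straight after a session.
3. In section 6.3, add a table of the number and percentage of patients with each symptom, by arm and session, with exact 95% confidence intervals and regardless of attribution. State that the comparison is descriptive.
4. Keep relation to VR as a secondary classification of the same events.

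The sponsor reporting rules in section 7 and the stopping text in section 6.4 need no change for this.

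The cost is a few extra questions for 15 to 17 control patients, who are already assessed after each session, and one extra table. The sample size and the visits stay as they are.
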